- 8) Children with multiple hormonal deficiencies must be on stable replacement therapy (stable dose and normal blood hormone levels) for other hypothalamo-pituitary axes for approximately 3 months. Thyroid replacement therapy for thyroid hormone deficiency must be instituted approximately 6 months (and be stable for approximately 3 months) prior to Screening. Temporary adjustment of glucocorticoid replacement therapy, as appropriate, is acceptable.
- 9) Normal 46 XX karyotype for girls (results prior to Screening may be accepted)
- 10) Written, signed informed consent of the parent(s) or legal guardian(s) of the subject and written assent of the subject (if the subject is able to read, understand, and sign)

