8.1.2 Exclusion Criteria

Exclusion criteria for this trial are as follows:

- 1) Children with a body weight below 12 kg
- 2) Prior exposure to recombinant hGH or IGF-1 therapy
- 3) Children with past or present intracranial tumor growth as confirmed by a sellar MRI scan (with contrast dye recommended) at Screening (MRI results from up to approximately 6 months prior to Screening may be accepted)
- 4) Children born SGA (ie, birth weight ≤ -2.0 SD for gestational age, with or without a birth length ≤ -2.0 SD for gestational age) (*Mandy 2016*)
- 5) Malnutrition, defined as:
 - Serum albumin level below the LLN according to the reference ranges of the central laboratory, and
 - Serum iron below the LLN according to the reference ranges of the central laboratory, and
 - BMI ≤ -2.0 SD for age and sex
- 6) Children with psychosocial dwarfism
- 7) Children with idiopathic short stature
- 8) Other causes of short stature such as coeliac disease (confirmed by anti-transglutaminase antibodies test), hypothyroidism, or rickets
- 9) History or presence of malignant disease; any evidence of present tumor growth; children with GHD and clinically cured tumors may be eligible after consultation with the Medical Expert
- 10) Any clinically significant abnormality likely to affect growth or the ability to evaluate growth (eg, chronic diseases like renal insufficiency, spinal cord irradiation)
- 11) Subjects with poorly controlled diabetes mellitus (HbA1c $\geq 8.0\%$) or diabetic complications

- 12) Known chromosomal abnormalities and other named medical syndromes known to impact growth (eg, Turner syndrome, Laron syndrome, Noonan syndrome, Prader-Willi syndrome, Russell-Silver syndrome, SHOX mutations/deletions and skeletal dysplasias) with the exception of septo-optic dysplasia
- 13) Closed epiphyses
- 14) Tanner stage >1 (scant pubic hair alone does not exclude the subject)
- 15) Concomitant administration of other treatments that may have an effect on growth such as anabolic steroids with the exception of hormone replacement therapies (thyroxine, hydrocortisone, desmopressin)
- 16) Children requiring glucocorticoid therapy (eg, asthma) who are taking a dose of greater than 400 µg/d of inhaled budesonide or equivalents for longer than 1 month during a calendar year
(Note: Approximately equivalent doses: fluticasone: 264 µg/d; beclomethasone: 504 µg/d; flunisolide 1,000 µg/d; triamcinolone: 1,000 µg/d; mometasone: 211 µg/d; ciclesonide 264 µg/d)

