9.9.2.1 Permitted Therapies

- Replacement therapy for pituitary deficiencies of other axes. As growth hormone may enhance the transformation of hydrocortisone to cortisone, the investigator may increase the dose of hydrocortisone replacement therapy if needed (eg, for anticipated stress).
- Glucocorticoid therapy for indications other than adrenal replacement (eg, asthma) may be administered in a dose equivalent to inhaled budesonide of not more than 400 µg/d for a maximum of approximately 1 month during 1 calendar year (approximate equivalent doses: fluticasone: 264 µg/d; beclomethasone: 504 µg/d; flunisolide 1,000 µg/d; triamcinolone: 1,000 µg/d; mometasone: 211 µg/d; ciclesonide 264 µg/d).
- Treatment for diabetes

- Over-the-counter vitamins, minerals or other dietary supplements only if their use is agreed to by the investigator.

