11. ADVERSE EVENTS, SERIOUS ADVERSE EVENTS, AND REPORTING

11.1. Adverse Events

11.1.1 Definition

An AE is defined as any untoward medical occurrence in a clinical investigation subject administered a pharmaceutical product and which does not necessarily have a causal relationship with this treatment. An AE can therefore be any unfavorable and unintended sign (including abnormal laboratory finding), symptom, or disease temporally associated with the use of a medicinal (investigational) product, whether or not related to that product. An AE can arise with any use (eg, use in combination with another drug), route of administration, formulation, or dose, including an overdose (ICH E6, 21 CFR Part 312.32).

Risks to trial subjects MAY include rare events of the types listed below. Some of these risks are due to taking the investigational drug TransCon hGH, but most are known or thought to be associated with approved hGH therapies such as Genotropin. In view of the investigational nature of TransCon hGH, possible risks are not necessarily limited to those listed:

- Headaches
- Muscle pain
- Joint stiffness
- High blood sugar (hyperglycemia)
- Sugar in the urine (glycosuria)
- Intracranial hypertension with papilledema, visual changes, headache, nausea, and/or vomiting has been reported in a small number of patients treated with somatropin products
- Edema, arthralgia, myalgia, nerve compression syndromes including carpal tunnel syndrome/paraesthesias
- Hypothyroidism - In patients with GHD, central (secondary) hypothyroidism may first become evident or worsen during somatropin treatment.
- Slipped Capital Femoral Epiphysis – these may occur more frequently in patients with endocrine disorders (including GHD or in patients undergoing rapid growth). Any pediatric patient with the onset of a limp or complaints of hip or knee pain during somatropin therapy should be carefully evaluated.
- Progression of Pre-existing Scoliosis - progression of scoliosis can occur in patients who experience rapid growth. Because somatropin increases growth rate, patients with a history of scoliosis who are treated with somatropin should be monitored for progression of scoliosis. However, somatropin has not been shown to increase the occurrence of scoliosis.
- Skin atrophy

- When somatropin is administered subcutaneously at the same site over a long period of time, tissue atrophy may result. This can be avoided by rotating the injection site [see Dosage and Administration].

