9.2 Clinical Laboratory Evaluations

Descriptive summaries of actual (absolute) values and changes from baseline values if applicable will be presented for the following by treatment and visit in both original and standard units for the Safety Population using central laboratories data:

- Biochemistry: sodium, potassium, calcium, phosphate, chloride, total bilirubin, alkaline phosphatase, lactate dehydrogenase (LDH), aspartate aminotransferase (AST), alanine aminotransferase (ALT), gamma glutamyl transferase (GGT), albumin, total protein, creatinine, urea nitrogen, uric acid, serum iron and transferrin
- Hematology: hemoglobin, leukocytes, differential blood count of leukocytes, platelet count
- Hormone Levels: thyroid status (TSH, fT4, and fT3 levels) and morning cortisol
- Glucose Metabolism: HbA1c, and fasting insulin and glucose, HbA1c.
- Lipid Metabolism: Total cholesterol, triglycerides, HDL and LDL

Laboratory values will be displayed in the data listings and those that are outside the normal range will be flagged, along with corresponding normal ranges. Any out-of-range values that are identified by the investigator as being clinically significant will be presented in a data listing. For each laboratory parameter, if applicable, shifts in assessments of abnormality from baseline to each post-baseline visit will be presented (shift tables) for data from central laboratories.

Data listings of laboratory will also be provided, displaying details of each laboratory test captured on the CRF for central and local laboratories separately.

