- Figure 51.5 SAFETY Shift in HbA1c Levels (%) from baseline to Week 52 for the TransCon hGH and the daily hGH treatment groups

- Figure 52.1 SAFETY Shift in Glucose Levels (mmol/L) from baseline to Week 5 for the TransCon hGH and the daily hGH treatment groups
- Figure 52.2 SAFETY Shift in Glucose Levels (mmol/L) from baseline to Week 26 for the TransCon hGH and the daily hGH treatment groups
- Figure 52.3 SAFETY Shift in Glucose Levels (mmol/L) from baseline to Week 52 for the TransCon hGH and the daily hGH treatment groups
- Figure 53.1 SAFETY Shift in FT4 Levels (ng/dL) from baseline to Week 13 for the TransCon hGH and the daily hGH treatment groups
- Figure 53.2 SAFETY Shift in FT4 Levels (ng/dL) from baseline to Week 26 for the TransCon hGH and the daily hGH treatment groups
- Figure 53.3 SAFETY Shift in FT4 Levels (ng/dL) from baseline to Week 52 for the TransCon hGH and the daily hGH treatment groups
- Figure 54.1 SAFETY Shift in Cortisol Levels (ug/dL) from baseline to Week 13 for the TransCon hGH and the daily hGH treatment groups
- Figure 54.2 SAFETY Shift in Cortisol Levels (ug/dL) from baseline to Week 26 for the TransCon hGH and the daily hGH treatment groups
- Figure 54.3 SAFETY Shift in Cortisol Levels (ug/dL) from baseline to Week 52 for the TransCon hGH and the daily hGH treatment groups
- Figure 55.1 SAFETY Shift in FT4 Levels (pmol/L) from baseline to Week 13 for the TransCon hGH and the daily hGH treatment groups
- Figure 55.2 SAFETY Shift in FT4 Levels (pmol/L) from baseline to Week 26 for the TransCon hGH and the daily hGH treatment groups
- Figure 55.3 SAFETY Shift in FT4 Levels (pmol/L) from baseline to Week 52 for the TransCon hGH and the daily hGH treatment groups
- Figure 56.1 SAFETY Shift in Cortisol Levels (nmol/L) from baseline to Week 13 for the TransCon hGH and the daily hGH treatment groups
- Figure 56.2 SAFETY Shift in Cortisol Levels (nmol/L) from baseline to Week 26 for the TransCon hGH and the daily hGH treatment groups
- Figure 56.3 SAFETY Shift in Cortisol Levels (nmol/L) from baseline to Week 52 for the TransCon hGH and the daily hGH treatment groups

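### Thyroid and cortisol safety summaries pool children with and without replacement of that axis, which dilutes any effect and leaves dose-corrected worsening uncounted

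*SAP*

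**What the plan says.** Thyroid status and morning cortisol are safety endpoints (Protocol 13.1.3, SAP 2.2.2). SAP 9.2 covers "Hormone Levels: thyroid status (TSH, fT4, and fT3 levels) and morning cortisol" and states that the descriptive summaries "will be presented for the following by treatment and visit in both original and standard units for the Safety Population using central laboratories data". It adds shift tables from baseline to each post-baseline visit. Tables 14.3.3.13.1 to 14.3.3.15 carry this out for hormone status. Figures 46-49 plot mean FT4 and cortisol over time, and Figures 53-56 plot their shifts, for example "Shift in FT4 Levels (ng/dL) from baseline to Week 52 for the TransCon hGH and the daily hGH treatment groups".

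Replaced children are in that population. Inclusion criterion 8 (Protocol 8.1.1) reads "Children with multiple hormonal deficiencies must be on stable replacement therapy (stable dose and normal blood hormone levels". Exclusion criterion 15 (Protocol 8.1.2) bars growth-affecting treatments "with the exception of hormone replacement therapies (thyroxine, hydrocortisone, desmopressin".

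The protocol also expects hormone status and replacement needs to move on treatment. Protocol 11.1.1 warns: "In patients with GHD, central (secondary) hypothyroidism may first become evident or worsen during somatropin treatment". Protocol 9.9.2.1 says that growth hormone may increase conversion of hydrocortisone to cortisone and that "the investigator may increase the dose of hydrocortisone replacement therapy if needed", giving anticipated stress as an example.

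**The concern.** On a replaced axis the laboratory value is largely a reading of the prescribed dose. Pooling such a child with unreplaced children has two consequences. First, the mean change and the percentage shifting to low are averaged over children who have little room to show an effect, so both shrink towards zero. Second, if need rises and the dose is raised before the value leaves the normal range, the hormone tables show normal to normal. That is worsening of the kind the protocol names, and the planned tables cannot tell it apart from no change.

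The SAP does define a group with multiple pituitary hormone deficiencies (section 8.5 and Appendix 1), but uses it only to summarise efficacy variables. At stake is how clearly the report can describe a risk named in the protocol, in each arm and between arms. The primary efficacy analysis is not touched.

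**Working it through.** The documents contain no figure on this point to reproduce: neither the number of replaced children nor an expected hormone change is stated. The check therefore compares the planned outputs with one another, then works an illustration on stated assumptions.

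**1. What each planned output shows**

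| Output | Shows | Does not show |
|---|---|---|
| Hormone summaries and figures (SAP 9.2, 13.4) | Mean and change by arm and visit | Any split by replacement status |
| Shift tables (SAP 9.2) | Low values at Weeks 13, 26 and 52 | Need met by a dose increase with the value in range |
| Concomitant medication (SAP 9.10) | Incidence by ATC class 2 and 4 | New starts as such; dose increases |
| Adverse events (Protocol 11.1.3, SAP 9.1) | Abnormal values that are symptomatic, clinically significant or need therapy | A dose change with in-range values, unless the investigator records worsening |
| Table 14.1.4.2 | Other pituitary deficiencies at baseline | Any link to hormone results |

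No row separates children by replacement status within a hormone result, and no row counts dose increases. The raw material exists: Protocol 9.9.2 requires changes in permitted medication to be recorded in the eCRF with dose, duration and indication.

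**2. Dilution**

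Let f be the share of an arm replaced on the axis, d the effect in unreplaced children and r the effect in replaced children. Then pooled effect = (1 - f) x d + f x r. If r = 0, this is (1 - f) x d. The values of f, a 10% incidence of new low values and a mean fall of 0.50 SD are all assumed. Arms are taken as 100 and 50.

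| f | Unreplaced (100 / 50) | 10% incidence appears as | 0.50 SD fall appears as |
|---|---|---|---|
| 5% | 95 / 47.5 | 9.5% | 0.475 SD |
| 10% | 90 / 45 | 9.0% | 0.45 SD |
| 20% | 80 / 40 | 8.0% | 0.40 SD |
| 30% | 70 / 35 | 7.0% | 0.35 SD |

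**3. Between-arm comparison**

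The minimisation factors are age, peak GH and gender (Protocol 7.1.2), not other deficiencies. Treating allocation as simple randomisation, the 95% chance range for the difference in replaced share is 1.96 x sqrt(f(1 - f)(1/100 + 1/50)):

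- f = 5%: 7.4 points
- f = 10%: 10.2 points
- f = 20%: 13.6 points
- f = 30%: 15.6 points

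With a true fall of 0.50 SD in unreplaced children of both arms and none in replaced children, an imbalance at that limit gives a spurious difference of 0.50 times the imbalance: 0.037, 0.051, 0.068 and 0.078 SD. The standard error of the arm difference is sqrt(1/100 + 1/50) = 0.173 SD. The distortion is thus under half a standard error even at f = 30%.

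**The case against.** A reader might infer that hormone loss is hidden: for example, that five children who fall low by Week 13 or 26 and are then treated would be reported as none. The documents do not support that.

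- Shift tables run to every post-baseline visit, Figures 53-56 show Weeks 13, 26 and 52 separately, and SAP 6.1.3 includes all data points in shift tables. Those five would be absent only from the Week 52 table, where a return to range on treatment is a correct result.
- Protocol 11.1.3 makes an abnormal value that requires therapy an adverse event and treats a worsened pretreatment condition as a new one. SAP 9.1 tabulates these by arm.
- New starts can be approximated. Prior medication is anything begun before the first dose (SAP 7.3), and concomitant medication is anything taken from the first dosing day (SAP 9.10). A new starter is only in the second table.
- The issue applies axis by axis. A child on thyroxine alone still has an informative cortisol. A child who enters in range on a stable dose and then falls below range at that dose also appears as a shift.
- The share replaced is an assumption, and so is zero change in replaced children. For cortisol, the protocol's remark on hydrocortisone conversion argues against exactly zero.

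All of this stands, and it limits the point to dilution plus one unseen category. It does not remove either. ATC classes do not reveal dose increases and are less specific for glucocorticoids. The shift tables use central-laboratory data, and no hormone sample is scheduled between Weeks 26 and 52. A deficit found and treated on a local sample in that interval therefore reaches the report through the adverse-event tables, not the shift tables.

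**Conclusion.** The point holds as a limited weakness in descriptive safety reporting. Pooling by axis shrinks any effect seen in unreplaced children by the share replaced, illustratively 5% to 30%. Worsening corrected by dose while values stay in range is not identifiable from any planned table. Chance imbalance between arms adds little.

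This rests on three assumptions. A replaced axis mainly reflects the dose; this is a premise of the argument, consistent with the entry requirement for normal levels on a stable dose, but not stated in the documents. Replaced children show no change. The range chosen for f is reasonable. A true share near zero would make the dilution negligible, and a non-zero change in replaced children would alter it. The case for acting is that the protocol names the risk and the remedy is cheap, not that a large bias has been shown.

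**What to change.** In SAP 9.2 and the table and figure index:

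1. Present the thyroid summaries, shift tables and figures by arm separately for children with and without thyroxine at baseline. Do the same for cortisol with and without hydrocortisone at baseline. Keep the pooled tables and show both strata, because the named risk includes worsening as well as new onset.
2. Leave the laboratory shift tables as measured. Add a separate descriptive count by arm of children with a new start or a sustained dose increase of thyroxine or hydrocortisone after the first dose, using the eCRF dose and indication. Report temporary or stress dosing on its own line.

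It may be tempting to recode a child as shifted to low once replacement is started or raised. That should be avoided: it would put open-label prescribing decisions, including stress dosing, into an objective laboratory table.

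One related tidy-up: SAP 9.2 promises central and local listings, but the listing index names hormone status for the local laboratory only (16.2.8.5). A central listing that shows replacement status would help.

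The cost is SAP wording and a few more descriptive outputs, with no new data and no change to patient care. The downside is small replaced strata: at f = 5% to 30%, about 5 to 30 children in the TransCon hGH arm and 2.5 to 15 in the Genotropin arm.

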9.3 Antibodies

The appropriateness of the approach taken to analyze and report anti-drug antibody data should be evaluated on a case-by-case basis [9], following recent regulatory guidances and white papers [10]. Statistical analysis of antibodies against drug (ADA) will include (but not be limited to) the following tabulated summaries of antibody frequencies and population percentages (for each cohort):

1. Incidence of pre-existing anti-hGH binding antibodies (positive Baseline)
2. Incidence of treatment induced anti-hGH binding antibodies by positive types (treatment emergent positive and treatment boosted positive) and overall
3. Incidence of persistent anti-hGH binding antibodies by positive types and overall
4. Incidence of transient anti-hGH binding antibodies by positive types and overall
5. Incidence of treatment induced anti-hGH neutralizing antibodies¹ by positive types and overall
6. Incidence of persistent anti-hGH neutralizing antibodies by positive types and overall
7. Incidence of transient anti-hGH neutralizing antibodies by positive types and overall
8. Incidence of pre-existing anti-PEG antibodies (positive Baseline)
9. Incidence of treatment induced anti-PEG binding antibodies by positive types and overall
10. Incidence of persistent anti-PEG antibodies by positive types and overall
11. Incidence of transient anti-PEG antibodies by positive types and overall

Neutralizing antibodies are defined as confirmed binding anti-hGH antibodies that are confirmed positive in a cell-based neutralizing antibody assay.

In addition, treatment induced anti-hGH binding, anti-hGH neutralizing antibodies, and anti-PEG antibodies will also be summarized by visit and positive types and overall.

Treatment induced ADA will include two positive types:

- Treatment emergent positive: if baseline (pre-treatment sample) is negative for ADA and post-treatment sample is positive for ADA
- Treatment boosted positive: if baseline (pre-treatment sample) is positive and post-treatment sample has a titer which is at least 4-fold higher than the pre-treatment sample.

Transient ADA is defined as treatment-induced ADA detected only at one sampling time point during study, or when there is less than 16 weeks between the first and the last ADA positive post-treatment samples.

Persistent ADA is defined as when there is more than (or equal to) 16 weeks between the first and the last ADA positive post-treatment samples.

9.4 Vital Signs

Descriptive summaries of actual values and changes from baseline will be calculated for Systolic Blood Pressure (SBP), Diastolic Blood Pressure (DBP), Heart Rate (HR), and Respiratory Rate (RR). These summaries will be presented by treatment, visit, and assessment time for the Safety Population.

A data listing of vital signs will also be provided, displaying details of each vital sign test captured on the CRF.

9.5 ECGs

Descriptive summaries will be presented for ECG measures of PR interval, RR interval, QRS interval, QT interval, and HR. These summaries will be presented by treatment group and visit.

The number and percentage of subjects with normal and abnormal ECG results (as per [Appendix 2](#)) will be summarized for the Safety Population by treatment group. For each ECG measure, if applicable, shifts in assessments of abnormality from baseline to each post-baseline visit will be presented (shift tables).

A data listing of ECG will also be provided, displaying details of each ECG measure captured on the CRF.

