14.3.4 Other Safety Data Summary Tables

Table 14.3.4.1	SAFETY	Summary of Vital Signs by Visit
Table 14.3.4.2	SAFETY	Summary of Electrocardiogram (ECG) Assessment by Visit
Table 14.3.4.3	SAFETY	Summary of Electrocardiogram (ECG) Data by Visit
Table 14.3.4.4	SAFETY	Electrocardiogram (ECG) Data: Shift in Assessments Compared to Baseline
Table 14.3.4.5	SAFETY	Summary of Bone Age
Table 14.3.4.6	SAFETY	Physical Examination Results by Body System and Visit
Table 14.3.4.7	SAFETY	Pubertal Status: Summary Assessment by Sex and Visit
Table 14.3.4.8.1	SAFETY	Local Tolerability from Site by Visit: Summary of Subjects with Injection Related Events
Table 14.3.4.8.2	SAFETY	Local Tolerability from Site by Visit and Severity: Summary of Subjects with Injection Related Events
Table 14.3.4.8.3	SAFETY	Local Tolerability from Site by Maximum Severity and Symptom for Overall Study: Summary of Subjects with Injection Related Events
Table 14.3.4.8.4.1	SAFETY	Local Tolerability from Patient Diary by Week - TransCon hGH: Summary of Subjects with Injection Related Events
Table 14.3.4.8.4.2	SAFETY	Local Tolerability from Patient Diary by Day - Genotropin: Summary of Subjects with Injection Related Events
Table 14.3.4.8.5.1	SAFETY	Local Tolerability from Patient Diary by Week and Severity - TransCon hGH: Summary of Subjects with Injection Related Events
Table 14.3.4.8.5.2	SAFETY	Local Tolerability from Patient Diary by Day and Severity - Genotropin: Summary of Subjects with Injection Related Events
Table 14.3.4.8.6	SAFETY	Local Tolerability from Patient Diary by Maximum Severity and Symptom for Overall Study: Summary of Subjects with Injection Related Events
Table 14.3.4.8.7	SAFETY	Exposure Adjusted Local Tolerability from Patient Diary for Overall Study
Table 14.3.4.8.8	SAFETY	Exposure Adjusted Local Tolerability from Patient Diary by Severity for Overall Study
Table 14.3.4.9	SAFETY	Concomitant Medication: Incidences by ATC Level 2 and 4
Table 14.3.4.10.1	SAFETY	Exposure to Study Treatment and Compliance
Table 14.3.4.10.2.1	SAFETY	Exposure to Study Treatment by Week – TransCon hGH
Table 14.3.4.10.2.2	SAFETY	Exposure to Study Treatment by Day – Genotropin
Table 14.3.4.10.3	SAFETY	Summary of Dose Timings
Table 14.3.4.10.4	SAFETY	Weight-based Planned Dosage (mg/dose) by Visit
Table 14.3.4.11	SAFETY	Serum concentration by Visit and PK analytes
Table 14.3.4.12	PK	Serum Concentration by Time Point and PK analytes at Visit: Individual data including Summary Statistics

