APPENDIX 2: ECG – NORMAL RANGES

For use on Pediatric Studies:

BMS uses global superimposed median beat as our preferred measurement methodology for pediatric studies. The Normal Range values below are based on this methodology.

Interval	Normal	Abnormal ECG, Not Clinically Significant	Abnormal ECG, Potentially Clinically Significant
HR 2 to < 6 years	80-140 bpm	60-79 bpm, or 141-180 bpm	< 60 bpm or >180 bpm
6 to < 12 years	60-120 bpm	50-59 bpm, or 121-150 bpm	< 50 bpm or >150 bpm
12 to < 18 years	50-100 bpm	40-49 bpm, or 101-150 bpm	< 40 bpm or >150 bpm
PR 2 to < 6 years	90-150 ms	Short if <90 ms, otherwise first degree AV block if 151-170 ms	> 170 ms
6 to < 12 years	100-170 ms	Short if <100 ms, otherwise first degree AV block if 171-190 ms	> 190 ms
12 to < 18 years	110-180 ms	Short if <110 ms, otherwise first degree AV block if 181-220 ms	> 220 ms
QRS 2 to < 6 years	≤ 90 ms with no QRS disturbance	91-100 ms with no QRS disturbance or IVCD or any QRS disturbance (except Left Posterior Fascicular Block) with a QRS ≤ 100 ms	IVCD or any QRS conduction disturbance with a QRS > 100 ms
6 to < 12 years	≤ 100 ms with no QRS disturbance	101-110 ms with no QRS disturbance or IVCD or any QRS disturbance (except Left Posterior Fascicular Block) with QRS ≤ 110 ms	IVCD or any QRS conduction disturbance with a QRS > 110 ms
12 to < 18 years	≤ 110 ms with no QRS disturbance	111-120 ms with no QRS disturbance or IVCD or any QRS disturbance (except Left Posterior Fascicular Block) with a QRS ≤ 120 ms	IVCD or any QRS conduction disturbance with a QRS > 120 ms
QTcF 0 to < 12 years	Males and Females: 320-450 ms	451-480 ms	QTcF > 480 ms
12 to < 18 years	Male: 320-450 ms	451-500 ms	QTcF > 500 ms
12 to < 18 years	Female: 320-470 ms	471-500 ms	QTcF > 500 ms
		All ages: Increase of QTcF (30 - 60 ms)*	All ages (male/female): Short QTcF < 320 ms All ages: Increase of QTcF (> 60 ms)*

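### SAP 9.5 summarises uncorrected QT but specifies no QTcF mean or change from baseline, although Appendix 2 classifies ECGs by QTcF and gives no range for QT

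*SAP*

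**What the plan says.** SAP 9.5 plans three kinds of summary output for ECGs.

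- **Descriptive summaries**, by treatment group and visit, for a named list: "Descriptive summaries will be presented for ECG measures of PR interval, RR interval, QRS interval, QT interval, and HR". No corrected QT appears in it, and the section does not mention change from baseline. SAP 9.4, on vital signs, does.
- **Normal/abnormal counts** for the Safety Population by treatment group: "The number and percentage of subjects with normal and abnormal ECG results (as per" Appendix 2).
- **Shift tables**: "For each ECG measure, if applicable, shifts in assessments of abnormality from baseline to each post-baseline visit will be presented". No measure is named in that sentence.

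Appendix 2 has rows for HR, PR, QRS and QTcF only. For children under 12 the QTcF normal range reads "Males and Females: 320-450 ms". Two categories concern a rise in QTcF: "All ages: Increase of QTcF (30 - 60 ms") in the lower abnormal column and "All ages: Increase of QTcF (> 60 ms") in the potentially clinically significant column.

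The matching entry for descriptive data in the SAP table list (Table 14.3.4.3) is titled "Summary of Electrocardiogram (ECG) Data by Visit". The title names no measures, and SAP section 14 puts the table shells in a separate document.

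**The concern.** The QT variable that is summarised has no classification range, and the QT variable that is classified is not listed for summary. Uncorrected QT depends on heart rate, so a change in mean QT mixes a repolarisation effect with a rate effect. Counts of abnormal ECGs pick up large excursions in single children. A modest shift across a whole arm shows in the mean change, and that output is not specified for QTcF.

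ECG is a named safety endpoint in both documents, and the protocol's schedules of events have every ECG after screening read centrally. The descriptive summary should therefore be able to show a rate-corrected result by arm.

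**Working it through.** **Step 1. Set the lists side by side.**

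| Measure | Descriptive list in 9.5 | Range in Appendix 2 |
|---|---|---|
| HR | yes | yes |
| PR | yes | yes |
| QRS | yes | yes |
| RR | yes | no |
| QT (uncorrected) | yes | no |
| QTcF | no | yes, plus two categories for an increase |

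The mismatch is confined to the last three rows.

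**Step 2. Which outputs does it reach?**

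- Descriptive summaries: QTcF is not specified.
- Normal/abnormal counts: these follow Appendix 2, so the QTcF limits and the 30-60 and >60 ms increases should be covered.
- Shift tables: there are two readings. If each ECG measure means the five listed ones, QT and RR drop out as not applicable because they have no range, and QTcF is missed. If it means the measures that Appendix 2 classifies, QTcF is included. The text does not settle which.

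**Step 3. Size of the rate effect.** The plan states no figure to reproduce. The Fridericia formula is inferred from the label QTcF, since the SAP does not write it out. The starting values, QTcF 400 ms and HR 100 bpm, are assumptions and do not come from the documents.

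Formula: QTcF = QT / (60/HR)^(1/3), so QT = QTcF × (60/HR)^(1/3).

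*QTcF held at 400 ms:*
- HR 100: QT = 400 × (60/100)^(1/3) = 337.4 ms
- HR 105: QT = 400 × (60/105)^(1/3) = 331.9 ms
- HR 110: QT = 400 × (60/110)^(1/3) = 326.8 ms

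A fall in rate from 110 to 100 bpm would thus lengthen QT by 337.4 − 326.8 = 10.6 ms with no change in QTcF. That is exaggeration.

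*QT held at 337.4 ms:*
- HR 100 to 105: QTcF = 400 × (105/100)^(1/3) = 406.6 ms, a rise of about 6.6 ms
- HR 100 to 110: QTcF = 400 × (110/100)^(1/3) = 412.9 ms, a rise of about 12.9 ms

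In both cases the QT row shows zero change. That is masking.

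**Step 4. Where masking stops being plausible.** For an unchanged QT to conceal a 30 ms rise from QTcF 400 ms, heart rate would have to rise by a factor of (430/400)^3 = 1.242, about 24%. A rate change of that size would show in the HR summary, and the Appendix 2 counts should flag the children concerned. The gap therefore matters for modest mean shifts, not for large ones.

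**The case against.** The strongest reply is that little is lost.

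- **QTcF is not absent from the ECG output.** A reader might infer from the five-measure list that it is. The documents do not support that: the list governs only the descriptive sentence, and the abnormality counts follow Appendix 2. This part of the reply stands in full.
- **The shift tables need not leave QTcF out.** The qualifier on applicability, placed directly after the reference to Appendix 2, allows a reading that includes it. This stands as far as ambiguity: omission is not shown, and neither is inclusion.
- **QTcF means may yet appear.** The shells are separate, SAP 6.2 allows further derived variables without amendment, and Protocol 13.4.5 foresees raw ECG statistics and change from baseline where appropriate. All true, but none of these names QTcF. Protocol section 13 also makes the SAP the analysis of record where the two differ.
- **HR and RR are summarised beside QT, and the arms are randomised with age in the minimisation.** Drift due to growth should therefore be similar in both arms, and a large rate shift would be visible, so calling mean QT uninterpretable would go too far. What remains is that the correction is applied per ECG and is non-linear, so mean QTcF and its change cannot be recovered exactly from group means of QT and RR.
- **Growth would not hide a QT effect.** A reader might expect that it would. The normal heart-rate ranges in Appendix 2 fall with age (80-140, 60-120, then 50-100 bpm), and a falling rate lengthens QT. Growth alone would exaggerate an apparent effect. Masking needs a rising rate, for which the documents give no specific reason.
- **Serial ECGs around peak exposure come only from a TransCon hGH subset of at least 8 children.** This limits what any mean from that profile can show, whichever QT measure is used.

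**Conclusion.** The point holds in a narrow form. SAP 9.5 lists uncorrected QT and not QTcF for descriptive summary, and it specifies no QTcF mean or change from baseline, while Appendix 2 relies on QTcF. A modest systematic QTcF shift could be masked or exaggerated in mean QT by a change in heart rate. In the illustration this is about 6.6 ms for 5 bpm and 12.9 ms for 10 bpm. Those figures rest on assumed starting values and on the Fridericia formula, and they say nothing about the heart rates expected in this trial.

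The documents do not support the wider conclusion that QTcF outliers would go uncounted or that the shift tables definitely leave QTcF out. Whether the table shells already show QTcF cannot be checked from these documents. The matter is minor: it concerns a descriptive safety summary and no efficacy claim.

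**What to change.** In SAP 9.5:

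1. Add QTcF, as value and change from baseline, to the measures summarised by treatment group and visit.
2. State that the shift tables use the Appendix 2 measures: HR, PR, QRS and QTcF.

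The existing QT and RR summaries can stay. The cost is about one sentence in the SAP and extra rows in tables already planned. QTcF must be available in any case to apply Appendix 2, so no new data are needed.
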